## 2.1 List of Recommended Images

### Parasternal long-axis window

1. 2D grayscale standard view (LV in a sagittal section)
2. 2D color Doppler for mitral regurgitation (MR)
3. 2D color Doppler of aortic (native or prosthetic) regurgitation (AR)
4. If AR is present, ZOOM & narrow sector with focus on vena contracta of regurgitant jet
5. 2D grayscale ZOOM for LV outflow tract diameter (LVOT)
6. Frozen image of measured LVOT diameter
7. 2D grayscale; ZOOM at an intercostal space higher for aortic root/aortic prosthesis

### Parasternal short-axis window

8. 2D grayscale LV at mitral valve level
9. 2D grayscale LV at papillary muscle level
10. Frozen image of measured LV dimensions (without measurements)
11. 2D grayscale LV at apical level
12. 2D grayscale aortic valve level
13. 2D color Doppler of AR: post-implant starts scanning from highest position and record first visible AR jet, scan more downwards and look for additional jets – confirm origin of AR jets from PLAX

### Parasternal long-axis view (RV inflow)

14. 2D color Doppler of tricuspid regurgitation (TR)
15. If TR is present, CW Doppler of TR jet (frozen image without measurements)
16. Frozen image of TR jet velocity with measurements

### Apical 4-Chamber window

17. 2D grayscale standard view
18. 2D color Doppler of MR
19. If MR is present, ZOOM & narrow sector
20. If MR is present, CW Doppler of MR jet (frozen image)
21. 2D color Doppler of TR
22. If TR is present, CW Doppler of TR jet (frozen image without measurement)
23. Frozen image of TR jet velocity with measurements
24. 2D grayscale focussed on LV with decreased depth
25. PW Doppler of transmitral flow at mitral valve tips (frozen image)
26. Tissue Doppler of the septal mitral annulus (frozen image)
27. Tissue Doppler of the lateral mitral annulus (frozen image)

### Apical long-axis view

28. 2D grayscale standard view
29. 2D color Doppler of AR
30. If AR is present, ZOOM & narrow sector, shift Nyquist 35-40 for PISA measurements
31. If AR is present, CW Doppler of AR jet (frozen image without measurement)
32. Frozen image of CW Doppler of AR jet (with measurements)
33. CW Doppler of aortic/prosthetic valve (frozen image without measurement)
34. Frozen image of measured aortic/prosthetic valve velocity

35. PW Doppler LVOT (native aortic valve): within 0.5 – 1 cm below native aortic valve (frozen image without measurements)
36. PW Doppler LVOT (post –implant) immediately proximal to inflow of stent or valve (frozen image without measurements)
37. Frozen image: measured LVOT velocity

**Apical 2-Chamber view**

38. 2D grayscale standard view
39. 2D grayscale focused on LV with decreased depth

**Sub-costal Position**

40. 2D grayscale; long-axis view
41. 2D grayscale; short-axis view
42. 2D grayscale: IVC and hepatic vein
43. If TR moderate by color Doppler, PW Doppler of hepatic vein (frozen image)
44. If AR mild by color Doppler, PW Doppler from descending aorta (frozen image)

**Supra-Sternal Position**

45. CW Doppler of aortic valve velocity non-imaging probe (frozen image without measurements)
46. Frozen image: measured aortic valve velocity
47. If AR mild by color Doppler, PW Doppler from descending aorta (frozen image)

**Right Parasternal Position**

48. CW Doppler of aortic valve velocity; non-imaging probe (frozen image without measurements)
49. Frozen image: measured aortic valve velocity

**Results Reporting**

50. Screen prints of all results pages

### 3.0 Data Requirements

Sites should obtain the appropriate images and Doppler recordings in order for the Echo Core Lab to assess and report the variables listed below. Procedures for acquiring key variables are described in Section 4, Acquisition of Key Variables.

- Height (cm) and Weight (kg)
- Heart rate
- Left ventricular outflow tract (LVOT) diameter in mid systole
- Max aortic/prosthetic valve velocity ( $V_2$ ) by CW Doppler
- Aortic valve velocity time integral (VTI) by CW Doppler
- Mean gradient across aortic valve ( $MGV_2$ ) by CW Doppler
- LVOT VTI by PW Doppler
- Grade of aortic/prosthetic transvalvular regurgitation (post-implant only)
- Grade of aortic/prosthetic paravalvular regurgitation (post-implant only)
- Grade of prosthetic total (transvalvular plus paravalvular) regurgitation (post-implant only)
- Grade of mitral regurgitation
- Grade of tricuspid regurgitation
- Max tricuspid regurgitant (TR) jet velocity (if TR is present)
- Left ventricular internal dimension at end diastole
- Left ventricular internal dimension at end systole
- Interventricular septal thickness at end diastole
- Left ventricular posterior wall thickness at end diastole
- Left atrial diameter (anterior-posterior linear dimension) at systole
- Left ventricular ejection fraction by visual estimate
- Grade of diastolic dysfunction (if present)

In addition, the following variables will be derived by the central database from the appropriate measurements reported on the site eCRF.

[figure not shown]
- Body surface area (Dubois and Dubois)
- Peak aortic pressure gradient
- Aortic valve area (AVA)/effective orifice area (EOA) by continuity equation
- Aortic valve area/effective orifice area index (EOAI)
- Doppler Velocity Index
- Estimated right ventricular systolic pressure (RVSP)

Derived variables will be displayed on the eCRF upon entry of the appropriate raw measurements. The pre-implant qualifying AVA must be based on the site reported variables for LVOT diameter, LVOT VTI, aortic valve VTI, height, and weight.

## 4.0 Acquisition of Key Variables

### 4.1 LVOT Diameter

Pre-implant LVOT diameter is measured from the inner edge to inner edge of the septal endocardium, and the anterior mitral leaflet in mid-systole (Figure A and B). Following implantation of the TAV, LVOT diameter is measured from the parasternal long-axis view, immediately proximal to the inflow aspect of the stent, and in mid systole (Figure C and D). Post surgical valve implantation, LVOT diameter is measured from the junction of the anterior sewing ring and the ventricular septum to the junction of the sewing ring and the anterior mitral valve leaflet (Figure 4E and F).

[figure not shown]
**Figure 4.** (A) and (B) Examples of measurement of pre-implant LVOT diameter. LVOT diameter is measured from the white-black interface of the septal endocardium to the anterior mitral leaflet, parallel to the aortic valve plane, approximately 0.5 cm below the level of the aortic annulus, and in mid systole (C) and (D) Post TAV implantation, LVOT diameter measurement is from outer edge to outer edge of the inflow aspect of the stent (E) and (F) post surgical valve implantation, LVOT diameter is measured from the junction of the anterior sewing ring and the ventricular septum to the junction of the sewing ring and the anterior mitral valve leaflet.

## 4.2 LVOT Velocity

LVOT velocity is recorded with PW Doppler from the apical position, in either the apical long-axis view or in the anteriorly angulated four-chamber view (or “5-chamber view”). For pre-implant exams, the PW sample volume should be positioned just proximal to the aortic valve, with care to avoid the zone of pre-valve acceleration (usually 0.5 to 1.0 cm proximal to the cusps, Figure A).

Post TAV implantation, the sample volume should be placed proximal to the inflow aspect of the stent. Full-screen imaging of the TAV should be used to verify positioning of the sample volume below the stent before switching to spectral Doppler mode (Figure C and D). Post surgical valve implantation, the sample volume should be placed proximal to the inflow aspect of the sewing ring.

[figure not shown]
The LVOT VTI is measured by tracing the modal velocity (middle of the dense signal) for use in the continuity equation.

**Figure 5 (A)** Sample volume placement just proximal to zone of pre-valve acceleration (*illustration by Mayo Clinic, used with permission*) **(B)** Optimal LVOT velocity signal showing a smooth spectral Doppler recording with a narrow velocity range at each time point **(C)** Illustration showing correct sample volume placement just proximal to inflow of TAV stent **(D)** Full-screen imaging of stent to ensure positioning of sample volume below the TAV stent.

### 4.3 Aortic Valve Velocities

Aortic valve velocity should be interrogated with CW Doppler from a minimum of 2 transducer positions (apical and either a parasternal or suprasternal position). The position that provides the highest velocity is used for measurements. A smooth velocity curve with a clear outer edge and maximal velocity should be recorded. The maximal velocity is measured at the outer edge of the dark signal; fine linear signals at the peak should not be included in measurements. The outer edge of the dark “envelope” of the velocity curve is traced to provide both the VTI for the continuity equation and the mean gradient (Figure ).

**Figure 6. (A)** Aortic valve velocities interrogated from multiple transducer positions (*illustration by Mayo Clinic, used with permission*) **(B)** CW Doppler of severe aortic stenosis showing tracing of the velocity curve from mean gradient and VTI, and measurement of max velocity.

### 4.4 Assessment of Prosthetic Aortic Regurgitation

An integrated exam approach using color flow, pulsed-wave (PW), and continuous-wave (CW) Doppler is used to assess the severity of transvalvular and paravalvular aortic regurgitation (AR). Color flow Doppler imaging should be performed from the parasternal long and short-axis views, and the apical long-axis and/or 5-chamber views. In the short axis view, color imaging should be performed at multiple levels (from level of the leaflets to below the skirt and frame to assess paravalvular regurgitation, and at the coaptation point of the leaflets for transvalvular (central) regurgitation).

If AR is seen by color Doppler, a CW Doppler recording of the regurgitant signal should be obtained for measurement of pressure half-time and assessment of jet density. If the degree of AR by color Doppler appears more than mild by visual estimate, the velocity in the proximal descending aorta should be recorded with PW Doppler.

The degree of transvalvular, paravalvular, and total (transvalvular plus paravalvular) AR will be graded as none, trace, mild, mild to moderate, moderate, moderate to severe, and severe based on the synthesis of the Doppler parameters shown in Table 17. The category of “trace” should be used in cases where regurgitation is barely detectable by color Doppler. Regurgitant signals observed to originate within the stent will be considered transvalvular, and regurgitant signals observed to originate outside the stent will be considered paravalvular.

**Table 17. Parameters for evaluation of the severity of aortic regurgitation**

3-class Grading Scheme	Trace	Mild	Mild	Moderate	Moderate	Severe
Unifying 5-Class Grading Scheme	Trace	Mild	Mild-to-Moderate	Moderate	Moderate-to-severe	Severe
Doppler parameters (qualitative or semiquantitative)						
Jet Features						
Extensive/wide jet origin	Absent	Absent	Absent	Present	Present	Present
Multiple jets	Possible	Possible	Often present	Often present	Usually present	Usually present
Jet path visible along stent	Absent	Absent	Possible	Often present	Usually present	Usually present
Proximal flow convergence visible	Absent	Absent	Absent	Possible	Often present	Often present
Vena contracta width (mm)	<2	<2	2-4	4-5	5-6	>6
Vena contracta area (mm  )	<5	5-10	10-20	20-30	30-40	>40
Jet width at origin (% LVOT diameter)	Narrow (<5)	Narrow (5-15)	Intermediate (15-30)	Intermediate (30-45)	Large (45-60)	Large (>60)
Jet density: CW Doppler	Incomplete or faint	Incomplete or faint	Variable	Dense	Dense	Dense
Pressure half-time (ms): CW Doppler	Slow (>500)	Slow (>500)	Slow (>500)	Variable (200-500)	Variable (200-500)	Steep (<200)
Diastolic flow reversal in descending aorta	Absent	Absent or brief early diastolic	Intermediate	Intermediate	Holodiastolic (end-diast. Vel. >20 cm/s)	Holodiastolic (end-diast. Vel. >25 cm/s)
Circumferential extent of PVR (%)	<10	<10	10-20	20-30	>30	>30
Doppler parameters (quantitative)						
Regurgitant volume (ml/beat)	<15	<15	15-30	30-45	45-60	>60
Regurgitant fraction (%)	<15	<15	5-10	10-20	20-30	>30
Effective regurgitant orifice area (mm  )	<5	<5	5-10	10-20	20-30	>30

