## 5.0 Core Lab Analysis

Protocol-required echocardiograms will be sent to the Echo Core lab for assessment: the data generated by the Echo Core Lab will be the primary data used for analysis and reporting. Received echocardiograms will be logged in and analyzed by the Echo Core Lab according to their procedures determined for this trial.

The Echo Core Lab will report the following variables:

- Heart rate
- Left ventricular outflow tract (LVOT) diameter in mid systole
- Max aortic/prosthetic valve velocity ( $V_2$ ) by CW Doppler
- Aortic valve velocity time integral (VTI) by CW Doppler
- Mean gradient across aortic valve ( $MGV_2$ ) by CW Doppler
- LVOT VTI by PW Doppler

- Grade of aortic/prosthetic transvalvular regurgitation (post-implant only)
- Grade of aortic/prosthetic paravalvular regurgitation (post-implant only)
- Grade of prosthetic total (transvalvular plus paravalvular) regurgitation (post-implant only)
- Grade of mitral regurgitation
- Grade of tricuspid regurgitation
- Max tricuspid regurgitant (TR) jet velocity (if TR is present)
- Left ventricular internal dimension at end diastole
- Left ventricular internal dimension at end systole
- Interventricular septal thickness at end diastole
- Left ventricular posterior wall thickness at end diastole
- Left atrial diameter (anterior-posterior linear dimension) at systole
- Left ventricular ejection fraction by visual estimate
- Grade of diastolic dysfunction (if present)

Qualitative grading of valvular regurgitation will be performed using the criteria described in Sections 4.4 through 4.7. For reporting the degree of prosthetic regurgitation, the grading classes may be collapsed according to the 3-class grading scheme recommended by the American Society of Echocardiography (ASE)-European Association of Cardiovascular Imaging Guidelines (Table 16).

In addition, the following variables will be derived by the central database from the appropriate measurements reported by the Echo Core Lab:

- **Peak Pressure Gradient (Peak  $\Delta P$ ) Across the Aortic Valve in mmHg**  
Peak  $\Delta P = 4 \times (V_2^2)$   
Where:  $V_2$  is the peak velocity across the prosthesis in m/sec
- **Aortic Valve Area (AVA) in  $\text{cm}^2$**   
AVA = LVOT diameter in  $\text{cm}^2 \times 0.785 \times (VTI_{V1}/VTI_{V2})$   

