### 3.0 Efficacy Event Definitions

PROSTHETIC VALVE DYSFUNCTION	
Stenosis: moderate/severe	Any of the following 1) Peak aortic velocity >4 m/s OR mean aortic gradient >40 mmHg, AND EOA <0.8 cm  . 2) Peak aortic velocity >4 m/s OR mean aortic gradient >40 mmHg, AND EOA ≥0.8 cm  , and DVI <0.25, 3) Peak aortic velocity ≤4 m/s and mean aortic gradient ≤ 40 mmHg, AND EOA <0.8 cm  , and DVI <0.25
Paravalvular regurgitation: moderate	Moderate paravalvular regurgitation (per echo criteria in Table 17, 3 grade scheme)
Paravalvular regurgitation: severe	Severe paravalvular regurgitation (per echo criteria in Table 17, 3 grade scheme) per echo criteria in CIP)
Transvalvular regurgitation: moderate	Moderate paravalvular regurgitation (per echo criteria in Table 17, 3 grade scheme)
Transvalvular regurgitation: severe	Severe transvalvular regurgitation (per echo criteria in Table 17, 3 grade scheme)
Total regurgitation: moderate	Moderate total regurgitation (per echo criteria in Table 16, 3 grade scheme)
Total regurgitation: severe	Severe total regurgitation (per echo criteria in Table 16, 3 grade scheme)

Notes:

1. DVI = Doppler Velocity Index (LVOT VTI/valve VTI)
2. For subjects with BSA <1.6 m^2, the EOA criteria for significant (moderate or severe) stenosis is <0.6 cm^2
3. For subjects with LVOT diameter >2.5 cm, the DVI criteria for significant (moderate or severe) stenosis is <0.2 cm^2
4. Reporting of prosthetic valve dysfunction will be based on core lab results.
5. Prosthetic valve dysfunction events are not reported as adverse events, unless the dysfunction is accompanied with clinical sequelae at the time of event detection, and the clinical sequelae are chronologically and physiologically associated with the dysfunction. However, prosthetic dysfunctions that are associated with adverse events, and that meet the definition of a serious adverse event, should be reported as such.

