**Confidential**

- Mean aortic gradient < 20 mmHg or peak velocity < 3 m/sec;
- Absence of moderate or severe prosthetic valve regurgitation. Total Aortic Prosthetic Regurgitation on the ECHO CORE LAB form not equal to moderate or severe.

All of the above components must be satisfied to count as a device success. If any of the above components fails, the endpoint will be counted as a failure.

For the overall device success rate, the numerator will be the number of subjects whose procedures result in device success as described above, and the denominator will be the number of subjects whose device success results are not missing (either success or failure). Note that this analysis excludes those subjects with a missing response to any of the above five components (eg, the field “Post-implant Severity of Total Aortic Regurgitation”=“Unable to Assess” or “Not Recorded”, missing mean aortic gradient, or missing peak velocity, etc.) and without a “NO” response to any of the components.

- Hemodynamic performance metrics by Doppler echocardiography
  - Mean aortic gradient at one year
  - Effective orifice area at one year
  - Degree of total, peri, and transvalvular prosthetic regurgitation at one year

For mean gradient and effective orifice area, the descriptive statistics will be reported at each of the assessed time point (30 days, 6 months, one year, 2 years, 3 years, 4 years, 5 years, 7 years and 10 years). The statistical method will be the Bayesian version of a two-sample t-test.

Prosthetic regurgitation severity will be reported as proportions at each of the assessed time point (30 days, 6 months, one year, 2 years, 3 years, 4 years, 5 years, 7 years and 10 years). The statistical method will be the Bayesian version of a comparison of proportions.

- New York Heart Association (NYHA) functional classification at one year

NYHA function classification will be reported as proportions at each of the assessed time point (30 days, 6 months, one year, 2 years, 3 years, 4 years, 5 years, 7 years and 10 years). The statistical method will be the Bayesian version of a comparison of proportions.

- Health-related quality of life as assessed by EQ-5D survey instrument at one year.

The endpoint will be evaluated using a Bayesian analog of a two-sample t-test.

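### The regurgitant fraction row of the aortic regurgitation grading table (Table 17) contradicts itself and the regurgitant volume row, so some mild leaks could be graded moderate

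*Protocol*

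**What the plan says.** Protocol Appendix I, Section 4.4, grades transvalvular, paravalvular and total prosthetic regurgitation "based on the synthesis of the Doppler parameters shown in Table 17". Section 5.0 of that appendix binds the core laboratory to the same criteria: "Qualitative grading of valvular regurgitation will be performed using the criteria described in Sections 4.4 through 4.7".

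Three quantitative rows of Table 17 matter here. In each, the columns run trace, mild, mild-to-moderate, moderate, moderate-to-severe, severe.

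- Volume: "Regurgitant volume (ml/beat) <15 <15 15-30 30-45 45-60 >60".
- Fraction: "Regurgitant fraction (%) <15 <15 5-10 10-20 20-30 >30".
- Effective regurgitant orifice area, in mm²: "<5 <5 5-10 10-20 20-30 >30".

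The six columns collapse to the reporting classes as "3-class Grading Scheme Trace Mild Mild Moderate Moderate Severe", so mild-to-moderate counts as mild and moderate-to-severe counts as moderate.

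The grade then feeds endpoints. Protocol Appendix V, Section 3.0, defines prosthetic valve dysfunction by the three-class grade, for example "Moderate paravalvular regurgitation (per echo criteria in Table 17, 3 grade scheme". SAP Section 6.8 makes the core-lab grade a component of device success: "Total Aortic Prosthetic Regurgitation on the ECHO CORE LAB form not equal to moderate or severe". The same SAP section compares regurgitation proportions between the arms.

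**The concern.** The fraction row looks like a transcription error. Its last four cells match a row in different units, and the sequence falls from under 15% for mild to 5-10% for the next grade up. A reader who applies it literally meets a moderate threshold of 10%, below the upper limit given for mild.

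The line between mild and moderate separates no event from an event in one-year valve-related dysfunction, and success from failure on the regurgitation component of device success. A threshold that is too low, or that two readers can resolve differently, would push some mild leaks over that line.

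Two smaller faults lie in the same chain. Appendix V, Section 3.0, defines moderate transvalvular regurgitation with the paravalvular wording. Its two total-regurgitation entries, and Section 5.0 of Appendix I, point to Table 16; the tables now carrying that number list device components.

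**Working it through.** **Inputs.** All cut-offs are from Protocol Table 17. The documents give no stroke volume, so 60 to 110 mL is an assumption, used only in step 4.

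| Row | Trace | Mild | Mild-to-moderate | Moderate | Moderate-to-severe | Severe |
|---|---|---|---|---|---|---|
| Volume (mL) | <15 | <15 | 15-30 | 30-45 | 45-60 | >60 |
| Fraction (%) | <15 | <15 | 5-10 | 10-20 | 20-30 | >30 |
| Orifice area (mm²) | <5 | <5 | 5-10 | 10-20 | 20-30 | >30 |

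**1. Cell comparison.** Fraction equals orifice area in four of six cells (mild-to-moderate to severe). The other two equal the volume row.

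**2. Overlap within each row.** Apart from the cut-off shared by trace and mild, the volume and orifice-area rows have no overlapping grades. The fraction row has two overlaps:

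- 5-10% is trace or mild and also mild-to-moderate. All of these are mild or less in the three-class scheme, so no endpoint changes.
- 10-15% is trace or mild and also moderate. A fraction of 12% is thus both a non-event and an event.

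This step uses nothing outside the table.

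**3. Agreement with the volume row.** Fraction = regurgitant volume / total (LVOT) stroke volume. The stroke volume at which two boundaries coincide is therefore volume / fraction:

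- mild-to-moderate to moderate: 30 / 0.10 = 300 mL
- moderate to moderate-to-severe: 45 / 0.20 = 225 mL
- moderate-to-severe to severe: 60 / 0.30 = 200 mL

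The upper limit for mild, by contrast, implies 15 / 0.15 = 100 mL. No single stroke volume reconciles the two rows.

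**4. A 20 mL leak over the assumed range.** By volume it is mild-to-moderate, hence mild in three classes.

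| Total stroke volume (mL) | Fraction | Grade by the fraction row | Three-class |
|---|---|---|---|
| 60 | 20/60 = 33.3% | severe | severe |
| 80 | 20/80 = 25.0% | moderate-to-severe | moderate |
| 90 | 20/90 = 22.2% | moderate-to-severe | moderate |
| 110 | 20/110 = 18.2% | moderate | moderate |

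Severe needs a total stroke volume below 20 / 0.30 = 66.7 mL. The fraction drops below the 10% moderate threshold only above 20 / 0.10 = 200 mL.

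**5. Choice of denominator.** The stroke volume above is total, not forward; the two differ by the regurgitant volume. If 75 to 90 mL were forward volume, the total would be 95 to 110 mL and the fraction 20/95 = 21.1% to 20/110 = 18.2%. That is still moderate or moderate-to-severe, and not severe.

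**The case against.** The strongest reply is that no rule lets fraction set the grade. Table 17 has 14 parameter rows, the grade is a synthesis, and Section 5.0 calls it qualitative. Regurgitant fraction, volume and orifice area are absent from the variables the core lab is listed as reporting and from the derived-variable formulas. A recommended PISA image means fraction could be derived, but nothing says that it will be. This stands: misgrading is a possibility of unknown frequency.

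The reach is also limited. No test in the labelling hierarchy (Protocol Section 3.3.3.7, SAP Section 6.9) uses a regurgitation grade, nor does the primary endpoint. The SAP table in Section 6.8 and event code 194 in Appendix V word transvalvular regurgitation correctly, so that slip adds little.

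What the reply does not answer is the contradiction itself. Synthesis cannot repair a criterion that assigns one measurement to three grades, because readers may resolve it differently. A layout fault is an unlikely explanation: the row has six entries under six column heads, and its neighbours are well formed.

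A reader might infer that mild leaks will commonly be called severe. The documents do not support that; it depends on a low stroke volume that they do not state. A reader might also infer a bias between the arms. The documents give no leak distribution by arm, and device success is estimated for TAVR only.

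**Conclusion.** The row is wrong as written and should be corrected. Two results are firm: the 10-15% overlap between trace or mild and moderate, and the mismatch with the volume row at 300, 225 and 200 mL. Both follow from the table, the second with the definition of regurgitant fraction.

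The upward direction for a 20 mL leak (18% to 33%, moderate or higher) rests on an assumed total stroke volume of 60 to 110 mL. Within that range, the severe reading holds only below about 67 mL.

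The number of exams affected cannot be computed, because the documents do not establish whether fraction was measured or allowed to decide a grade. The exposed results are one-year valve dysfunction, the regurgitation proportions and TAVR device success. This is a defect in secondary-endpoint criteria with a cheap remedy, and it does not threaten the trial's main conclusion.

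**What to change.** 1. Reconcile the regurgitant fraction row with the source cited for Table 17 (Protocol reference 67) and with the volume row, or remove fraction from the grading criteria. No replacement cut-offs are proposed here, because the documents do not give them.
2. In Appendix V, Section 3.0, correct the entry for moderate transvalvular regurgitation to match SAP Section 6.8.
3. Redirect the Table 16 references in Appendix I, Section 5.0, and in the two total-regurgitation entries of Appendix V, to Table 17.
4. Have the core lab state in writing whether fraction was used and with which cut-offs. Re-grade only the exams where fraction decided the grade.

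The cost is one table row, one definition line, three cross-references and a core-lab confirmation. If fraction was never used, no re-grading follows.
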